8.3 Primary Efficacy Endpoint and Analyses

8.3.1 Primary Efficacy Endpoint

The primary efficacy endpoint is endoscopic improvement (Mayo endoscopic subscore of 0 or 1) at Week 8. Note that evidence of friability during endoscopy in subjects with a Mayo endoscopic subscore of 0 or 1 will confer an endoscopic subscore of 2.

8.3.2 Handling of Missing Data for the Primary Efficacy Endpoint

For the primary analysis, NRI-C will be used for missing data imputation.

8.3.3 Primary Analysis of the Primary Efficacy Endpoint

Analysis of the primary efficacy endpoint will be conducted on the FAS. Comparison of the primary efficacy endpoint will be performed between the ravagalimab group and the historical placebo group using Bayesian approach with placebo distribution [REDACTED] from historical data meta-analysis and prior for ravagalimab Beta (0.5, 0.5), the Jeffrey's prior for binomial distribution. The posterior probability of rate difference > 0 given data, i.e., $P(\theta_{ABBV-323} - \theta_{Placebo} > 0 | data)$ will be calculated. In addition, the mean difference and 95% credible interval for the mean difference will be provided.

8.3.4 Sensitivity and Supplementary Analysis of the Primary Efficacy Endpoint

The same Bayesian approach will be also conducted based on the FAS using AO data as a sensitivity analysis.

As a supplementary analysis for the primary efficacy endpoint, the following approach will be used. For more details, see [Appendix D](#).

1. Bayesian approach using [REDACTED] prior for placebo group and Beta(0.5, 0.5) prior for treatment group. Note [REDACTED]
[REDACTED]

In addition, point estimate and 95% CI using normal approximation will be provided for the response rate for the ravagalimab group using NRI-C and AO data.

8.3.5 Additional Analyses of the Primary Efficacy Endpoint

In addition, a set of synthetic placebo subjects will be created from Bio-IR placebo subjects of Upadacitinib UC Study M14-234 (Substudy 1, ph2b and Substudy 2, ph3) based on the similarity of inclusion/exclusion criteria and definitions of efficacy endpoints of the studies.

A logistic regression with potential firth adjustment model with being treated as the outcome will be performed using treatment subjects in Study M15-722 and placebo subjects from the two historical Study M14-234 Substudy 1 and Study M14-234 Substudy 2. Selected common baseline demographics and disease characteristics variables among all the three studies will be included as predictive covariates in the model. See [Appendix E](#) for the full list. Propensity score for each subject will be the estimated probability of being treated conditional on the covariates.

A 1:1 matched placebo group will be generated from the above set of synthetic placebo subjects using "greedy matching" i.e., nearest neighbor matching without replacement within a pre-specified caliper distance 0.2 of the standard deviation of the logit of the propensity scores, to match the treatment subjects in Study M15-722. Other matching ratios or calipers may also be considered to preserve matched number of patients and considering the similarity with historical data. If multiple placebo subjects have propensity scores that are equally close to that of the treated subject, one of these placebo subjects will be selected at random. Subjects who are not selected in the matching process will be excluded from data analysis. Pairwise comparison between the matched treatment and placebo groups will be performed for primary endpoints using the Cochran-

Mantel-Haenszel (CMH) test stratified by baseline corticosteroid use (yes, no) and Mayo endoscopic subscore (2 vs 3). NRI-C will be used to handle missing data.

As a sensitivity analysis, 1:1 matched placebo group will be generated from the above set of synthetic placebo subjects using optimal matching to match the treated subjects in Study M15-722.

Additional analysis based on stratification on the propensity score may also be performed. All the subjects including synthetic placebo subjects in the logistic regression model will be ranked according to their estimated propensity score. Subjects are then stratified into five equal-size groups based on the treatment arm using the quintiles of the estimated propensity score. Pairwise comparison between the treatment and synthetic placebo groups will then be performed using the Cochran- Mantel-Haenszel (CMH) test stratified by the quintiles of the estimated propensity score, baseline corticosteroid use (yes, no) and Mayo endoscopic subscore (2 vs 3). NRI-C will be used to handle missing data.

8.4 Secondary Efficacy Endpoint and Analyses

For binary endpoints, point estimate and 95% CI using normal approximation will be provided for the response rate for the ravaglimab using NRI-C and AO data. The same Bayesian approach specified in Section 8.3.3 will be also conducted based on the FAS using NRI-C and AO data, if applicable.

The same additional analyses specified in Section 8.3.5 will be also conducted for secondary endpoints. Point estimate, 95% CI and p-value will be provided for the treatment comparison between ravaglimab and the placebo group based on the CMH test adjusting for baseline corticosteroid use (yes vs no) and Mayo endoscopic sub-score (2 vs 3).

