## 4 INVESTIGATIONAL PLAN

### 4.1 Overall Study Design and Plan

---

Study M15-722 is a Phase 2a, multicenter, single arm, open-label (OL) study to investigate the efficacy and safety of ravaglimab in subjects with moderate to severe UC who failed prior therapy. The study contains a 35-day screening period, 2 treatment periods, and an 84-day follow up period from the last dose of study drug. The induction period is an open-label 12-week treatment period to evaluate the efficacy, safety, tolerability, PK and RO of ravaglimab for inducing endoscopic improvement at Week 8. Subjects who achieve clinical response per Partial Adapted Mayo score at Week 12 may continue into the maintenance period. The maintenance period is an OL 92-week treatment period to assess efficacy and safety for maintenance of response with ravaglimab.

Prior to protocol version 4.0 the study had a double-blind (DB) placebo-controlled induction period. Ongoing subjects enrolled prior to version 4.0 continued their treatment as randomized during the induction period and, in case of clinical response at Week 12, their OL treatment during the maintenance period.

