3.3 Additional Efficacy Endpoints

Additional efficacy endpoints are:

- Change from Baseline in modified Baron score over time (at visits with endoscopy)
- Achievement with stool frequency subscore (SFS) = 0, rectal bleeding subscore (RBS) = 0, and Mayo endoscopic subscore = 0 over time (at visits with endoscopy)
- Time to clinical response per Partial Adapted Mayo score
- Endoscopic improvement over time (at visits with endoscopy)
- Clinical remission per Adapted Mayo score over time (at visits with endoscopy)
- Clinical response per Adapted Mayo score at over time (at visits with endoscopy)
- Clinical remission per Partial Adapted Mayo score over time
- Clinical response per Partial Adapted Mayo score over time
- Clinical remission per Adapted Mayo score over time among subjects who were taking corticosteroids at Baseline and subsequently discontinued corticosteroids for \geq 90 days prior to the respective visit
- Discontinuation of corticosteroid use for subjects taking corticosteroids at Baseline at all visits over time
- Endoscopic remission over time (at visits with endoscopy)
- Clinical remission per Full Mayo score over time in subjects with a Full Mayo score of 6 to 12 at Baseline (at visits with endoscopy)
- Clinical response per Full Mayo score over time in subjects with a Full Mayo score of 6 to 12 at Baseline (at visits with endoscopy)

- Achievement of SFS ≤ 1 over time
- Achievement of RBS = 0 over time
- Change from Baseline in RBS over time
- Change from Baseline in SFS over time
- Change from Baseline in fecal calprotectin (FCP) over time
- Change from Baseline in high sensitivity C-reactive protein (hs-CRP) over time
- Change from Baseline in Inflammatory Bowel Disease Questionnaire (IBDQ) over time
- UC-related Hospitalizations (yes/no) over time
- UC-related surgeries (yes/no) over time
- No bowel urgency over time
- Change from Baseline in weekly abdominal pain score over time
- Achievement of $\geq 30\%$ reduction from Baseline in weekly abdominal pain score over time
- Achievement of Weekly abdominal pain score = 0 over time
- Change from Baseline in number of extraintestinal manifestations (EIM) over time (as captured in the EIM electronic case report form [eCRF])
- Histologic remission over time (at visits with endoscopy)
- Mucosal healing (endoscopic and histologic remission) over time (at visits with endoscopy)

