8.2 Handling of Missing Data

Missing data imputation will be done only for efficacy variables (categorical and continuous variables). For the analysis other than efficacy, no imputation will be done for missing values.

Censoring

For the time-to-event endpoint, i.e., time to clinical response per Partial Adapted Mayo score, missing data will be considered as censored at the last available time for the information.

Non-Responder Imputation incorporating Multiple Imputation to handle missing data due to COVID-19 (NRI-C)

The NRI-C will categorize any subject who does not have an evaluation during a pre-specified visit window (either due to missing assessment or due to early withdrawal from the study) as a non-responder for the visit. In addition, at or after the UC-related corticosteroids intercurrent event (see Section 8.1), subjects will be counted as non-responders. The only exception is that missing data due to COVID-19 infection or logistical restrictions related to the COVID-19 pandemic will be handled by Multiple Imputation (MI). At each visit, subjects will be characterized as responders or non-responders based on MI imputed values if missing due to COVID-19; otherwise, subjects will be considered as non-responders for missing due to other reasons in the NRI-C approach.

Mixed-Effect Model Repeated Measurements (MMRM)

MMRM analysis will be conducted using mixed-effect model including observed measurements at all visits. For the MMRM analysis, data collected at or after UC-Related corticosteroids intercurrent event will be excluded. The mixed model includes the categorical fixed effects of visit, baseline corticosteroid use (yes vs no), baseline Mayo endoscopic sub-score (2 vs 3), the continuous fixed covariate of baseline measurement and treatment and treatment-by-visit interaction, if applicable. An unstructured variance covariance matrix will be used. If there is a convergence issue, a compound symmetry structure and a variance components structure will be considered in sequence. The parameter estimations are based on the assumption of data being missing at random and using the method of restricted maximum likelihood (REML).

As Observed (AO)

The AO analysis will not impute values for missing evaluations, and thus a subject who does not have an evaluation on a scheduled visit will be excluded from the AO analysis for that visit. All observed data will be used in the analysis.

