8.5 Additional Efficacy Analyses

Additional endpoints defined in Section 3.3 will be summarized at scheduled time points.

Additional Efficacy Analyses for Induction Period

For additional binary endpoints, point estimate and 95% CI using normal approximation will be provided for the response rate of the ravagalimab group using NRI-C and AO data.

For additional continuous endpoints, the LS-mean and 95% CI will be reported for the ravagalimab group using MMRM model and ANCOVA model based on AO data with baseline corticosteroid use (yes vs no) and baseline Mayo endoscopic sub-score (2 vs 3) as the fixed factors and the corresponding baseline value as the covariates.

For selected additional binary endpoints, point estimate and 95% CI using normal approximation will be provided for the response rate of ravagalimab and matched placebo group. Point estimate, 95% CI and p-value will be provided for the treatment comparison between ravagalimab and the matched placebo group based on the CMH test adjusting for baseline corticosteroid use (yes vs no) and Mayo endoscopic sub-score (2 vs 3).

For selected additional continuous endpoints, the LS mean and 95% CI will be reported for ravagalimab and matched placebo group. The LS mean treatment difference and associated 95% CI and p-values between ravagalimab and matched placebo group will be provided using MMRM model. For the MMRM analysis, data collected at or after UC-Related corticosteroids intercurrent event will be excluded. Supplementary analysis will be conducted based on ANCOVA model using AO data, with treatment, baseline corticosteroid use (yes vs no) and baseline Mayo endoscopic sub-score (2 vs 3) as the fixed factors and the corresponding baseline value as the covariates.

Additional Efficacy Analyses for Maintenance Period

Descriptive statistics will be provided for the ravagalimab group. These include the number of observations, mean, standard deviation, 95% CI, median, minimum, and maximum for continuous endpoints using AO data; and frequencies and percentages with 95% CI using normal approximation for binary endpoints using AO data.

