Table 7 shows the false positive rate and true positive rate for different assumed true placebo response rates and ravagalimab response rates given the historical placebo response rate is [REDACTED] respectively. Note the range of this placebo rate is determined by the 90% confidence interval of placebo rate based on meta-analysis. False positive rate is calculated as the probability that the posterior probability of rate difference > 0 is larger than 90% assuming there is no treatment difference between ravagalimab and placebo. True positive rate is calculated as the probability that the posterior probability of rate

difference > 0 is larger than 90% assuming there is a 25% treatment difference between ravagalimab and placebo.

[REDACTED] prior corresponds to borrowing [REDACTED] subjects with a historical placebo rate of [REDACTED] and [REDACTED] prior corresponds to borrowing [REDACTED] subjects with a historical placebo rate of [REDACTED]. Operating characteristics of using [REDACTED] prior are the similar as using [REDACTED] prior based on the calculation.

Based on [Table 7](#), within 90% confidence interval of placebo rate [REDACTED] 20 historical subjects or less could be borrowed while controlling false positive rates $< 10\%$ and not exceeding in study sample size.

D3. Comparison between ravagalimab and Placebo.

Posterior probability of rate difference [REDACTED] given the endoscopic improvement at Week 8 results, i.e., [REDACTED] will be calculated as follows. [REDACTED] are the response rates of ravagalimab and placebo, respectively.

Let n and N be the number of responders and number of subjects at Week 8. The conjugate priors used for [REDACTED] are [REDACTED] respectively. Therefore the posterior distributions for $\theta_{\text{ravagalimab}}$ and θ_{Placebo} will be [REDACTED] respectively. Note that in primary analysis, the

response rate is estimated using NRI-C which incorporates MI to handle missing data due to Covid-19; then the number of responders (n) is calculated based on the total number of subjects and estimated response rate, without rounding to an integer, to calculate the posterior probability.

Then the posterior probability is given by

$$\text{Posterior Probability} = \frac{\text{Beta}(n + \text{Beta prior}, m + \text{Gamma prior})}{\text{Beta}(n + \text{Beta prior}, m + \text{Gamma prior}) + \text{Beta}(n + \text{Beta prior}, m + \text{Gamma prior})}$$

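### The SAP's only interval for a single-group response rate is an unnamed normal approximation at N of about 40 or fewer; if it is Wald, it under-covers badly near 0% and 100%

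*SAP*

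**What the plan says.** The SAP uses one kind of interval for a response rate in a single group:

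- Primary endpoint (SAP 8.3.4): "point estimate and 95% CI using normal approximation will be provided for the response rate for the ravagalimab group", on NRI-C and AO data.
- Secondary endpoints (SAP 8.4): "point estimate and 95% CI using normal approximation will be provided for the response rate for the ravaglimab using NRI-C and AO data".
- Additional endpoints, induction (SAP 8.5): the same for ravagalimab. For selected endpoints the interval is also given "using normal approximation will be provided for the response rate of ravagalimab and matched placebo group".
- Maintenance (SAP 8.5): "frequencies and percentages with 95% CI using normal approximation for binary endpoints", on AO data only.

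No section says which normal-approximation interval is meant, and no exact, Wilson or other small-sample interval appears. The one zero-responder rule, in SAP Appendix D3, drops the Bayesian comparison when both observed rates are zero. It does not reach these intervals. The credible interval in SAP 8.3.3 is for the difference from placebo, not for the ravagalimab rate.

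The planned sample is up to about 40 (SAP 2.4), with an interim analysis at 30 (SAP 11.0). AO analyses drop subjects without an evaluation (SAP 8.2). The maintenance cohort is smaller and selected: "Subjects who achieve clinical response per Partial Adapted Mayo score at Week 12 may continue into the maintenance period" (Protocol 4.1).

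**The concern.** The Wald interval is unreliable when the expected number of responders or non-responders is small. With no responders its width is zero, and with few its lower limit can be negative. At low rates it errs mainly by setting the upper limit too low.

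Low rates are realistic here. The endpoints include endoscopic remission, mucosal healing, all three subscores equal to zero, and "UC-related surgeries (yes/no) over time". The disclosed historical placebo counts are 2/161 for Full Mayo remission (SAP Table 6) and 4/65, 4/65 and 11/161 for endoscopic improvement (SAP Appendix D1). A weakly active drug could therefore give very few responders. Rates near 100% can arise in maintenance, because only Week 12 responders enter it.

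At stake is the precision shown in the tables. The objective is exploratory, and the interim is meant to inform later Phase 2b and 3 planning. For maintenance endpoints, and for additional binary endpoints not selected for the matched comparison, the reader has no other interval.

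**Working it through.** **Plan's own figure.** The documents state no coverage for these intervals. The 3.1% in Protocol 7.3 belongs to the Bayesian rule and rests on a redacted prior. This point does not depend on it.

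**Inputs.** n = 40 (SAP 2.4) and 30 (SAP 11.0). The maintenance n is not given, so 20 and 15 are assumptions (30 also serves as one). Disclosed historical rates are 2/161 = 1.24% and (4 + 4 + 11)/(65 + 65 + 161) = 19/291 = 6.5%. The design alternative is placebo plus 25 points, about 31% if placebo is about 6%; the planned placebo rate is redacted. *Normal approximation* is taken as the uncorrected Wald interval.

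**Formulas**, with p = x/n and z = 1.96:

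- Wald: p ± z√(p(1−p)/n)
- Wilson: [p + z²/(2n) ± z√(p(1−p)/n + z²/(4n²))] / (1 + z²/n)
- Exact coverage at true rate θ: the sum of Binomial(x; n, θ) over all x whose interval contains θ

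**Examples**

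- 0/40: Wald 0 ± 0. Wilson upper limit z²/(n + z²) = 3.84/43.84 = 8.8%.
- 3/40: Wald 0.075 ± 1.96 × √(0.075 × 0.925/40) = 0.075 ± 0.082, or −0.7% to 15.7%. Wilson 2.6% to 19.9%.
- 0/20: Wald 0% to 0%; Wilson upper limit 16.1%. 20/20: Wald 100% to 100%; Wilson 83.9% to 100%.

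**Why coverage collapses.** At θ = 2/161 the chance of 0/40 is (1 − 0.0124)^40 = 0.607. Each such sample gives an interval of zero width that misses θ, so coverage cannot exceed 39.3%.

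**Exact coverage, n = 40, nominal 95%**

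| True rate | Wald | Wilson |
|---|---|---|
| 1.24% (2/161) | 39% | 91% |
| 2% | 55% | 95% |
| 5% | 87% | 95% |
| 6.5% (19/291) | 92.9% | 95.6% |
| 8% | 84% | 96% |
| 31% | 93.7% | 96.2% |
| Average, 1–10% | 79% | 95.6% |
| Average, 10–20% | 91.8% | 95.3% |
| Average, 20–60% | 93.7% | 95.1% |

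Of the Wald misses, 12.9 of 13.2 points at 5% and 15.9 of 16.3 points at 8% are upper limits that are too low.

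**Smaller n, average over 1–10% (by symmetry also 90–99%)**

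| n | Wald | Wilson |
|---|---|---|
| 30 | 74.4% | 95.7% |
| 20 | 62.6% | 95.6% |
| 15 | 53.5% | 95.3% |

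A continuity correction does not cure this: at n = 40 it gives 55.4% at 2% and 87.1% at 5%.

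**NRI-C.** Under SAP 8.2, "subjects will be characterized as responders or non-responders based on MI imputed values if missing due to COVID-19", so the pooled rate need not correspond to a whole number of responders. Appendix D3 accepts this for the Bayesian analysis: "the number of responders (n) is calculated based on the total number of subjects and estimated response rate, without rounding to an integer". The Wilson formula also takes a non-integer rate. It was simulated with 100,000 trials per rate, N = 40, 20 imputations from a Beta(x + 0.5, n − x + 0.5) posterior and data missing at random. None of these settings is in the SAP. Wilson used the pooled rate, with n equal to the number of subjects not imputed.

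| True rate | Wilson, 2 missing | Wilson, 4 missing | Wald with Rubin variance, 2 missing |
|---|---|---|---|
| 2% | 95.9% | 96.5% | 58.0% |
| 5% | 96.0% | 96.7% | 85.5% |
| 6% | 97.0% | 95.3% | 89.6% |
| 8% | 97.1% | 96.0% | 87.4% |
| 31% | 94.9% | 95.3% | 92.5% |

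No figure is given for the matched placebo group, because the M14-234 counts are redacted.

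**The case against.** **The SAP never says Wald.** The Wilson interval also rests on a normal approximation. This stands: what the text establishes is that the interval is not named, and the under-coverage is conditional on the usual reading. If Wilson was meant, naming it settles the matter.

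**The intervals decide nothing.** The study is an exploratory proof of concept without multiplicity control, and the primary inference is a posterior probability. Secondary endpoints also have a CMH comparison with its own interval and, where applicable, the Bayesian comparison. This stands and limits the importance of the point. It does not help the maintenance endpoints or the unselected additional endpoints.

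**The worst figures come from very low rates.** At 6.5%, the disclosed placebo rate for the primary endpoint, Wald coverage is 92.9%, which is tolerable. True, but coverage oscillates with the rate: 87% at 5% and 84% at 8%. The 79% average over 1–10% is the fairer summary.

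**Wilson has faults too.** At low rates its misses fall on the other side, with lower limits too high: 8.8% of samples at 1.24%, 4.6% at 2% and 4.8% at 5%, against at most 0.3% for Wald at these rates. Its lowest coverage over 1–10% is 89.7% at n = 40 and 83.7% at n = 15. This is a real cost, but small beside Wald minima of 33.1% and 14.0%.

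**Other intervals would serve.** Clopper-Pearson is conservative (average 98.4% over 1–10% at n = 40). Jeffreys averages 95.6% and matches the Beta(0.5, 0.5) prior already in the SAP. Either would be defensible if named.

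**Conclusion.** The concern holds. The SAP leaves the interval unnamed, and its usual reading gives misleading precision for rates near 0% or 100% at these sample sizes. At n = 40 average coverage over 1–10% is 79% rather than 95%, and it is lower for smaller maintenance cohorts. At rates of 20–60% the shortfall is only one to two points. Point estimates, the Bayesian analysis and the CMH comparisons are untouched, so this is a change worth considering rather than a threat to the trial's conclusions.

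The result assumes the uncorrected Wald form. The maintenance figures assume n, and the NRI-C figures assume an imputation model. The exact coverage figures at n = 40 and n = 30 need no assumption beyond Wald and binomial sampling.

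**What to change.** In SAP 8.3.4, 8.4 and 8.5, replace the normal approximation with the Wilson score interval, for ravagalimab and matched placebo rates alike.

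- **AO data:** use the observed responder count and the number of subjects observed at that visit.
- **NRI-C data:** apply Wilson to the pooled rate, with n equal to the number of subjects whose status at that visit was not set by multiple imputation. This is ordinary Wilson when nothing is missing because of COVID-19.

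The NRI-C rule is stable across imputation seeds. With no observed responder and 2 of 40 imputed, the upper limit is 9.2%. It is 9.4% if one subject is imputed as a responder in one of 20 imputations, and 97.5% of simulated seeds are at or below 9.6%. With 4 of 40 imputed the range is 9.6% to 10.5%.

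No separate rule for 0/N or N/N is then needed, because Wilson gives a usable interval in both cases.

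The cost is SAP wording and table programming, with a closed formula and no new data. The intervals are no longer symmetric about the estimate, and upper limits rise when responders are few (3/40: from 15.7% to 19.9%).
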